### **CMT-HI**

For the total CMT-HI and subgroup scores, the effect of ACE-083 administered during the open-label extension compared to the treatment administered in the double-blind placebo-controlled phase will be examined for those receiving ACE-083 during the double-blind phase and separately for those receiving placebo during the double-blind phase by comparing the absolute change observed between Day 190 and pre-first treatment baseline (1st 6 months) and Day 358 versus Day 190 (2nd 6 months) using an ANCOVA model.

Covariates to be included into the model are SEQUENCE, CMT-TYPE, and BASELINE where:

- SEQUENCE represents the treatment sequence from double blind to open-label (ACE-083 → ACE-083 or Placebo → ACE-083)
- CMT-TYPE refers to the type of CMT (e.g. CMT1 or CMTX)
- BASELINE represents the baseline value of the parameter of interest from the double-blind phase

Least squares estimates of the SEQUENCE effect and 90% confidence intervals will be provided.

If the Day 358 and/or Day 190 assessments have no missing data, then the above ANCOVA model will be used for analysis. If missing data is present, a standard multiple imputation with the above ANCOVA model will be used for analysis as described in [Section 4.11.1](#).

The statistical analysis described above will be done on the Per Protocol Set and will be considered primary. The analyses described above will also be repeated for the Full Analysis Set.

In addition, a line graph of the mean ± SEM of the absolute change from baseline will be provided by sequence for each scheduled time.

Additional analyses may be performed as appropriate.

## CMTES2

For the CMTES2 score, the effect of ACE-083 administered during the open-label extension compared to the treatment administered in the double-blind placebo-controlled phase will be examined for those receiving ACE-083 during the double-blind phase and separately for those receiving placebo during the double-blind phase by comparing the absolute change observed between Day 190 and pre-first treatment baseline (1st 6 months) and Day 358 versus Day 190 (2nd 6 months) using an ANCOVA model.

Covariates to be included into the model are SEQUENCE, CMT-TYPE, and BASELINE where:

- SEQUENCE represents the treatment sequence from double-blind to open-label (ACE-083 | ACE-083 or Placebo | ACE-083)
- CMT-TYPE refers to the type of CMT (e.g. CMT1 or CMTX)
- BASELINE represents the baseline value of the parameter of interest from the double-blind phase

Least squares estimates of the SEQUENCE effect and 90% confidence intervals will be provided.

If the Day 358 and/or Day 190 assessments have no missing data, then the above ANCOVA model will be used for analysis. If missing data is present, a standard multiple imputation with the above ANCOVA model will be used for analysis as described in [Section 4.11.1](#).

The statistical analysis described above will be done on the Per Protocol Set and will be considered primary. The analyses described above will also be repeated for the Full Analysis Set.

In addition, a line graph of the mean  $\pm$  SEM of the absolute change from baseline will be provided by sequence for each scheduled time.

Additional analyses may be performed as appropriate.

## Gait

For each type of measurement recorded (i.e. “General measures”, “Gait cycle phase measures”, “Gait assessment range of motion”, and “Gait assessment foot drop”), the effect of ACE-083 administered during the open-label extension compared to the treatment administered in the double-blind placebo-controlled phase will be examined for those receiving ACE-083 during the double-blind phase and separately for those receiving placebo during the double-blind phase by comparing the absolute change observed between Day 190 and pre-first treatment baseline (1st 6 months) and Day 358 versus Day 190 (2nd 6 months) by descriptive statistics. This will also be done for the average absolute change from baseline for assessments performed on the left and right sides.

The effect of ACE-083 on the average absolute change for mid-swing foot angle administered during the open-label extension compared to the treatment administered in the double-blind placebo-controlled phase will be examined for those receiving ACE-083 during the double-blind phase by comparing the average absolute change observed between Day 190 and pre-first treatment baseline (1st 6 months) and Day 358 versus Day 190 (2nd 6 months) using an ANCOVA model.

Covariates to be included into the model are SEQUENCE, CMT-TYPE, and BASELINE where baseline represents the baseline from the double-blind phase and SEQUENCE and CMT-TYPE are defined similarly as for MVIC.

Least squares estimates of the SEQUENCE effect and 90% confidence intervals will be provided.

A line graph of the mean  $\pm$  SEM will be provided by sequence for each scheduled time for the average absolute change for mid-swing foot angle.

Additional analyses may be performed as appropriate.

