For the MVIC value and decimal MMT-MRC score for each side treated as well as the average from the left and right sides, CMTES2 score, CMT-HI total score and selected subscale scores, and motor function test assessments, raw data and changes from baseline (percent and absolute change) from baseline will be summarized by treatment for each scheduled time using descriptive statistics. In addition, a mixed model will be fitted to assess the treatment effect (ACE-083 vs. placebo) using a 2-sided 0.10 significance level for the percent change from baseline. Least squares estimates of the treatment effect and corresponding 90% confidence intervals will be provided. In addition, least squares estimates of the treatment effect and corresponding 90% confidence intervals will be provided for patients having dorsiflexion MMT-MRC grade of 4- to 4+ on both sides.

Additional analyses may be performed as appropriate.

Open-label extension

For the MVIC value and decimal MMT-MRC score for each side treated as well as the average from the left and right sides, CMTES2 score, CMT-HI total score and selected subscale scores, and motor function test assessments, raw data and changes (percent and absolute change) from the start of the open-label extension (Day 190) will be summarized by treatment for each scheduled time using descriptive statistics.

Additional analyses may be performed as appropriate.

Open-label extension vs. double-blind placebo-controlled phase

For the MVIC value [average from the left and right sides] decimal MMT-MRC score [average from the left and right sides], CMTES2 score, CMT-HI total score and selected subscale scores, and motor function test assessments, the effect of ACE-083 administered during the open-label extension compared to the treatment administered in the double-blind placebo-controlled phase will be examined for those receiving ACE-083 during the double-blind phase and separately for those receiving placebo during the double-blind phase by comparing the absolute and/or percent

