**4.7.2.2.3. Open-Label vs. Double-Blind Placebo-Controlled Period****MVIC**

The effect of ACE-083 administered during the open-label extension compared to the treatment administered in the double-blind placebo-controlled phase will be examined for those receiving ACE-083 during the double-blind phase and separately for those receiving placebo during the double-blind phase by comparing the average absolute and/or percent changes [depending on the parameter] observed between Day 190 and pre-first treatment baseline (1st 6 months) and Day 358 versus Day 190 (2nd 6 months) using an ANCOVA model.

Possible covariates to be included into the model are SEQUENCE, MRC-MMT SCORE, CMT-TYPE and BASELINE where:

- SEQUENCE represents the treatment sequence from double blind to open-label (ACE-083 → ACE-083 or Placebo → ACE-083)
- MRC-MMT SCORE represents the conversion of the screening MRC-MMT grade to the decimal version as follows: 5 = 5.0, 5- = 4.67, 4+ = 4.33, 4 = 4.0, 4- = 3.67, 3+ = 3.33, 3 = 3.0, 3- = 2.67, 2+ = 2.33, 2 = 2.0, 2- = 1.67, 1+ = 1.33, 1 = 1.0
- CMT TYPE refers to the type of CMT (e.g. CMT1 or CMTX)
- BASELINE represents the baseline value from the double-blind phase

Least squares estimates of the SEQUENCE effect and 90% confidence intervals will be provided.

If the Day 358 and/or Day 190 assessments have no missing data, then the above ANCOVA model will be used for analysis. If missing data is present, a standard multiple imputation with the above ANCOVA model will be used for analysis as described in [Section 4.11.1](#).

In addition, a line graph of the mean ± SEM of the percent change from baseline will be provided by sequence for each scheduled time.

Additional analyses may be performed as appropriate.

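### The open-label versus double-blind model for mid-swing foot angle is limited to one treatment sequence, so the SEQUENCE effect it promises cannot be estimated

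*SAP*

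**What the plan says.** SAP 4.7.2.2.3, Gait, has two analysis paragraphs. The first is descriptive. It covers all gait measures and compares the two six-month periods in patients who had ACE-083 in the double-blind phase and, separately, in those who had placebo.

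The second gives an ANCOVA for one gait measure, mid-swing foot angle. Its population is the ACE-083 group alone: the effect "will be examined for those receiving ACE-083 during the double-blind phase by comparing the average absolute change observed between Day 190" and baseline with that from Day 190 to Day 358. It continues: "Covariates to be included into the model are SEQUENCE, CMT-TYPE, and BASELINE where baseline represents the baseline from the double-blind phase". For the other two terms, "SEQUENCE and CMT-TYPE are defined similarly as for MVIC". The MVIC definition is that "SEQUENCE represents the treatment sequence from double blind to open-label (ACE-083 → ACE-083 or Placebo → ACE-083"), which is two levels. The only model output named is: "Least squares estimates of the SEQUENCE effect and 90% confidence intervals will be provided". A line graph "will be provided by sequence for each scheduled time for the average absolute change for mid-swing foot angle".

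The parallel sections name both groups. CMTES2, for example, has the ACE-083 group "and separately for those receiving placebo during the double-blind phase by comparing the absolute change observed" over the same two intervals. Protocol 14.2.3 plans the same comparison for motor function tests in the ACE-083 group and separately in "those receiving placebo during the double-blind phase by comparing the absolute and/or percent" changes, and protocol 12.4 lists gait among those tests.

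**The concern.** The stated population and the stated output do not fit together. SEQUENCE distinguishes patients by their double-blind treatment. Once the population is fixed by that treatment, SEQUENCE no longer varies, and a factor with one level has no effect to estimate.

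The restriction also removes from the model the group in which the comparison contrasts drug with placebo. In placebo to ACE-083 patients, the second six months set against the first is active treatment against placebo. In ACE-083 to ACE-083 patients it is continued treatment against initial treatment. Mid-swing foot angle is the measure that SAP 4.7.1.2 files under foot drop, and it is the only gait parameter given a model.

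A programmer following the text must either report something other than the promised estimate or choose the population at the time of analysis. The SAP is meant to settle such choices before database lock.

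**Working it through.** **Inputs.** Planned arm sizes are 20 ACE-083 and 20 placebo (SAP 3.2), with 18 per arm expected to complete the double-blind period (SAP 4.1.1). The model terms are SEQUENCE, CMT-TYPE and BASELINE (SAP 4.7.2.2.3, Gait), and SEQUENCE has two levels (same section, MVIC).

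**The plan's own figure.** The Gait section states no number, so only the arm sizes matter here, and they reproduce. With a two-sided 0.10 level, 90% power, a 10% difference and an SD of 10%, n per arm = 2 × (1.645 + 1.282)² × (10/10)² ≈ 17.1, which rounds up to 18. The exact t-test power at 18 per arm is 0.902, and 36 / (1 − 0.10) = 40.

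**Estimability.** Write the model for patient i as

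Y_i = b0 + b1·SEQ_i + b2·CMT_i + b3·BASE_i + e_i,

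with SEQ_i = 1 for ACE-083 to ACE-083 and 0 for placebo to ACE-083. In the stated population SEQ_i = 1 for everyone. Then b0 and b1 enter only as the sum b0 + b1, and the data cannot separate them. The rank of the design matrix confirms this:

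| Patients in the model | Columns | Rank | Residual df | SEQUENCE effect |
|---|---|---|---|---|
| 20 ACE-083 only (as written) | 4 | 3 | 20 − 3 = 17 | not estimable |
| 18 ACE-083 only | 4 | 3 | 18 − 3 = 15 | not estimable |
| 20 + 20, both sequences | 4 | 4 | 40 − 4 = 36 | estimable |
| 18 + 18, both sequences | 4 | 4 | 36 − 4 = 32 | estimable |

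Stacking the two six-month changes of the 20 ACE-083 patients (40 rows) still gives rank 3 from four columns. Adding a PERIOD term to the stacked data gives five columns and rank 4: the period contrast becomes estimable and SEQUENCE still does not. BASELINE and CMT-TYPE values were simulated, with both CMT types present. The rank deficit comes from SEQUENCE being constant and does not depend on those values.

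**Patients outside this model.** 40 − 20 = 20, the whole placebo to ACE-083 sequence, or 20/40 = 50% of planned Part 2 patients.

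**Would naming the placebo group be enough?** That depends on what separately means. With one model per group, SEQUENCE is constant in each, and each has the same rank of 3 from four columns. With one model for both groups, SEQUENCE is estimable, but the listed covariates contain no PERIOD term and the response is not defined as a difference between the two intervals. The within-group comparison of second with first six months is then not produced. The parallel sections (MVIC, MRC-MMT, 10-meter walk/run, 6-minute walk, Berg, CMT-HI, CMTES2, TMV, and CCMV/FF/CIMF) share this ambiguity.

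**Deliberate or accidental?** SEQUENCE as a covariate, the SEQUENCE effect as output, the by-sequence graph and the descriptive paragraph all presuppose both groups. Protocol 14.5 says that deviations from its analyses will be indicated in the SAP. SAP Section 5 does have an item on this very comparison, but it changes only the confidence level, from 95% to 90%. An omitted phrase is the likelier explanation.

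**The case against.** The strongest reply is that this is a drafting slip in one exploratory, uncontrolled, supplementary model, and that the surrounding text shows what was meant. That is probably so, and it limits the importance of the point. The paragraph still cannot deliver what it promises as written.

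Three stronger readings are tempting, and the documents support none of them.

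- A reader might infer that placebo to ACE-083 patients drop out of the gait analysis altogether. They do not. The descriptive comparison of the two periods covers both groups for every gait measure, including foot drop, the graph is by sequence, and SAP 4.7.2.2.2 summarises open-label gait by treatment.
- A reader might infer that the model yields no estimate at all. Only the between-sequence contrast is lost. If the response is the within-patient difference between periods, its adjusted mean in the ACE-083 to ACE-083 group is estimable, with 17 residual degrees of freedom at 20 patients. Protocol 14.2.3 itself describes the effect as second against first six months within each group. The SAP, however, names the SEQUENCE effect as its output.
- A reader might infer that the evidence on foot drop is compromised. ACE-083 against placebo for mid-swing foot angle is already modelled in the randomised double-blind period (SAP 4.7.2.2.1, Gait), with 90% and 95% intervals. The before-and-after contrast in the placebo to ACE-083 group is open-label and confounded with time, so it can only add to that result.

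**Conclusion.** The point holds, within narrow limits. As written, the mid-swing foot angle ANCOVA in SAP 4.7.2.2.3 cannot provide the between-sequence SEQUENCE effect or its 90% interval, and it leaves out up to 20 of 40 planned patients. The first conclusion is algebraic and needs no assumption beyond the SAP's two-level definition of SEQUENCE. The second takes the planned arm sizes at face value, and dropout before Day 358 would lower the count.

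Gait is an exploratory objective in Part 2. No primary or secondary endpoint, significance level or sample size is affected, and neither is the randomised gait comparison. It is worth correcting before database lock because the rule fails if followed, it contradicts its own section and the protocol, and the related ambiguity runs through the parallel sections.

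**What to change.** In the second paragraph of SAP 4.7.2.2.3, Gait:

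1. State that patients from both sequences enter one ANCOVA.
2. Define the response as the within-patient difference between the two changes: (Day 358 − Day 190) − (Day 190 − baseline), averaged over left and right sides.
3. Keep SEQUENCE, CMT-TYPE and BASELINE as covariates.
4. Report the least squares mean of that difference with its 90% interval for each sequence, and the SEQUENCE contrast with its 90% interval. The means answer the within-group question in protocol 14.2.3, and the contrast is the output that the SAP already names.

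Do not stop at adding the placebo group with the wording of the parallel sections. If that wording is read as one model per group, SEQUENCE remains constant in each. Make the same clarification in the parallel parts of 4.7.2.2.3 (MVIC, MRC-MMT, 10-meter walk/run, 6-minute walk, Berg, CMT-HI, CMTES2) and 4.8.2.2.3 (TMV, and CCMV/FF/CIMF), with each section's own scale and covariates.

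The cost is a short SAP text edit. Protocol Table 6 already schedules gait at Day 1, Day 190 and Day 358 for all Part 2 patients, so no data or visits are added.

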### **Activity Level**

Exploratory analyses may be performed as appropriate.

#### **4.7.2.3. Other Analyses**

The number and percentage of patients belonging to each of the following criteria will be summarized by treatment group:

- Day 190 percent change in TMV from baseline  $\geq 10\%$
- Day 190 percent change in 6MWD from baseline  $\geq 10\%$
- Day 190 absolute change in 6MWD from baseline  $\geq 30$  m
- Day 190 percent change in time to complete 10mW/R from baseline  $\leq -10\%$
- Day 190 absolute change in time to complete 10mW/R from baseline  $\leq -0.5$  sec.
- Day 190 absolute change in CMT-HI total score from baseline  $\leq -8$
- Day 190 absolute change in CMT-HI mobility subscale score from baseline  $\leq -8$
- Day 190 absolute change in CMT-HI activities subscale score from baseline  $\leq -8$
- Day 190 absolute change in ankle dorsiflexion MRC-MMT decimal score  $\geq 0.16$
- Percent change in number of falls during Weeks 13 to 24 from the number of falls during Weeks 1 to 12  $\leq -20\%$

For each criterion listed above, Fisher's exact test will be used to compare the proportions of patients belonging to the individual criterion between the two treatment groups using a 0.1 significance level.

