Prior to the initiation of Part 2, a review of safety and efficacy data from Part 1 will be conducted by the SRT to determine the recommended dose level (maximum 250 mg/muscle). A total of up to 40 new patients may be enrolled and randomized (1:1 randomization) to receive either Clinical Study Protocol Study A083-03 Revision: 03 ACE-083 (n=20) or placebo (n=20) bilaterally by injection into both TA muscles. Patients will receive blinded study drug once every 3 weeks for approximately 6 months (9 doses).

Patients who complete the double-blind treatment period will immediately roll over to open-label treatment of ACE-083, receiving the same dose of active drug, bilaterally in the TA muscle, once every 3 weeks for approximately 6 months (8 doses). In Part 2, the SRT will periodically review blinded safety data for each muscle treated.

Justification for Dose Level 7.2.

ACE-083 was administered into either the rectus femoris (RF) or TA muscle of healthy post-menopausal women in the Phase 1 Study A083-01 at absolute dose levels per muscle of up to 200 mg (RF) or 150 mg (TA) as either a single dose or repeated dose every 3 weeks. The estimated ACE-083 (mg/g muscle) within the muscle was calculated using the dose administered to each patient and the size of each patient's RF muscle as measured by baseline MRI. The highest dose of ACE-083 evaluated (200 mg x 2 doses for RF; 150 mg x 2 doses for TA) produced a mean increase from baseline in muscle volume of 14.5% and 8.9% for RF and TA, respectively, at 3 weeks following the last dose. These dose levels were considered safe and generally well tolerated.

A starting dose level of 150 mg/muscle is considered appropriate and safe based on the Phase 1 clinical trial results. This starting dose level will protect patient safety and also ensure that the initial exposures achieved within the muscle have the potential to impact efficacy endpoints. All subsequent dose levels (higher or lower) will be determined following review of study data and recommendations from the SRT. A maximum absolute dose level of 250 mg/muscle following dose escalation has been chosen based on administration feasibility and volume constraints.

7.3. **Benefit/Risk Assessment**

Information about the known and expected benefits, risks, SAEs, and reasonably anticipated AEs of ACE-083 is provided in the IB.

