**Table 1: Planned Doses to be Administered for Part 1**

Cohort	Dosing Days	Muscle	Planned Dose Level	Type of Administration	ACE-083 n
1	1, 22, 43, 64, and 85	Tibialis Anterior	150 mg	Bilateral	6
2	1, 22, 43, 64, and 85	Tibialis Anterior	200 mg	Bilateral	6
3	1, 22, 43, 64, and 85	Tibialis Anterior	240 mg	Bilateral	6
Total Number of Patients (Planned)					18

Periodic reviews of selected blinded safety and imaging data will be reviewed by the Safety Review Team (SRT) in accordance with the SRT Guidelines.

#### 3.2. Part 2

Prior to the initiation of Part 2, a review of the safety and efficacy data from Part 1 will be done in order to determine the recommended dose level. Up to 40 patients will be enrolled and randomized (1:1 ratio) to receive either ACE-083 (n=20) or placebo (n=20) bilaterally. Patients will receive study drug once every three weeks for approximately 6 months (9 doses). If a patient discontinues the study for reasons other than a safety issue related to investigational study drug and the patient had not completed the Day 43 visit, the patient may be replaced. The replacement patient will receive the same treatment as the patient replaced.

Patients who complete the double-blind treatment period will immediately roll over to open-label treatment with ACE-083. All patients will receive ACE-083 administered at the same dose as in the double-blind period. They will receive bilateral injections, once every three weeks for approximately 6 months (8 doses). In Part 2, the SRT will periodically review the blinded safety data.

A stratified randomization schedule will be prepared under the direction of the Sponsor with the stratification factor of “CMT disease type” (values are CMT1 and CMTX). Because Part 2 is multicenter, an Interactive Response Technology (IRT) system will be used to randomize patients sequentially across clinical sites.

Similar to Part 1, periodic reviews of selected blinded safety and imaging data will be reviewed. Further details concerning the frequency and timing of SRT reviews of Part 2 data are described in the SRT Guidelines.

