## 4.2. Analysis Population

The analysis populations include the following:

- Full Analysis Set: Part 1 – All patients enrolled in the study receiving at least one dose of ACE-083. Part 2 – All patients randomized who have received at least one dose of study drug (includes placebo);
- Safety Set: All patients enrolled/randomized in the study who have received at least one dose of study drug (includes placebo);
- Per Protocol Set: All patients enrolled/randomized in the study who have received at least one dose of study drug (includes placebo) with no data or study procedural related issues that would otherwise impact the interpretability of the efficacy and/or pharmacodynamic data.

Such issues include but are not necessarily limited to:

- Patients who discontinue the study prior to the Dose 3 Day 43 visit; these patients may have been replaced per protocol
- Patients whose Day 1 MRI or Day 190 MRI was done 7 or more days following study drug administration
- Patients who did not receive the full study drug administration planned per protocol at all injection sites on any or both sides (right or left) for 2 or more consecutive visits for reasons other than dose reductions for the safety of the patient or feasibility concern (i.e., the site intended to administer the full dose but was unable).

- Patients whose Screening cumulative distance walked at 6 minutes is greater than 500 meters or less than 150 meters.

A review of the patient data will be performed and a list of patients to be excluded from the Per Protocol Set along with the reason for exclusion will be completed before the data is locked and unblinded.

Statistical analyses of efficacy and pharmacodynamics data will be performed on the Per Protocol Set (primary analysis population) and the Full Analysis Set (secondary analysis population). Analyses of safety data will be performed on the Safety Set. Should the statistical analysis populations be identical (e.g., Full Analysis Set = Per Protocol Set), statistical analyses will not be duplicated or repeated.

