### 4.4.2. Baseline Characteristics

Baseline characteristics of the patient population consist of selected items from the CMT disease history, MRI, MRC-MMT, and functional test data. Such data includes the following:

- Age at onset of symptoms (years)
- Age at diagnosis (years)
- Duration since onset of symptoms (years)
  - Duration since onset of symptoms = Age (years) – Age at onset of symptoms (years)
- Duration since diagnosis (years)
  - Duration since diagnosis = Age (years) – Age at diagnosis (years)
- Total muscle volume (mm^3)
  - See [Section 4.8.1](#) for definition.
- Total muscle mass (g)
  - See [Section 4.8.1](#) for definition.
- Calculated contractile muscle volume (mm^3)
  - See [Section 4.8.1](#) for definition.
- Calculated contractile muscle mass (g)
  - See [Section 4.8.1](#) for definition.
- Fat fraction (%)
- 6-minute walk distance (m)
- Time to complete 10 meter walk/run (s)

- Number and percent of patients belonging to specified CMT Type (i.e., CMT1, CMTX)
- Number and percent of CMT1 patients belonging to specified CMT1 subtype/gene mutation (e.g., CMT1A, CMT1B)
- Number and percent of CMTX patients belonging to specified CMTX subtype/gene mutation (e.g., CMTX1)
- Number and percent of patients belonging to specific forms of CMT (e.g., demyelinating, axonal, mixed)
- Number and percent of patients with first degree relatives with CMT
- Number and percent of patients who have fallen to the ground in the past 6 months
- Number and percent of patients who have had past history of fractures
- Number and percent of patients who have had past surgery for CMT
- Number and percent of patients who wears any lower limb orthotics/braces
- Number and percent of patients who uses assistive devices
- Number and percent of patients who have a regular (at least once a week) exercise program
  - For those who have a regular exercise program, the type (aerobic, resistance training, or both) and frequency of exercise program (1-2, 3-4, or 5+ times per week) will also be summarized.
- Number and percent of patients who have known nerve conduction velocity
  - For those who have a known nerve conduction velocity, the category ( $< 38$  m/s,  $\geq 38$ ) will also be summarized.
- Number and percent of patients with MRC-MMT grades belonging to the following categories: [3 to 4-], [4 to 4+], [5- to 5]

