### **Falls**

Individual data on the number and type of falls recorded in 4-week time intervals along with details on the timing and classification of the individual falls recorded, type of assistance, and information related to input (whether the fall was recorded by device detection or recorded by the individual patient) will be provided in a listing.

The number of falls, as well as the number of patients who fell at least once occurring from Week 1 to Week 24 (6 months) will be summarized by treatment group. Summaries will be provided for the additional subintervals between Weeks 1 and 24 as outlined in [Section 4.7.1.2](#). A record of “Near-fall” will not be counted as a “Fall”.

The hazard ratio of recurring falls between ACE-083 and placebo between Weeks 1 and 24 will be estimated using the Andersen-Gill recurrent events model with the following covariates: TREATMENT, CMT-TYPE, and ankle dorsiflexion MRC-MMT decimal score where the covariates are defined similarly as what was described for MVIC. The point estimate, p-value and 90% confidence interval for the hazard ratio for TREATMENT will be provided.

Additional methods for the statistical analysis of the recurring event of falls may be considered and performed as appropriate (e.g. negative binomial regression with similar covariates as listed for the Andersen-Gill recurrent events model described above).

No imputations will be performed for missing data.

The statistical analyses described above will be done on the Per Protocol Set and will be considered primary. The analyses described above will also be repeated for the Full Analysis Set.

Additional analyses may be performed as appropriate.

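### The falls responder criterion uses an on-treatment window (Weeks 1 to 12) as its reference, so it is insensitive to a benefit that starts early and lasts, and it has no rule for patients with no falls in that window

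*SAP*

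**What the plan says.** SAP 4.7.2.3 lists ten responder criteria and compares the proportions meeting each one "between the two treatment groups using a 0.1 significance level", using Fisher's exact test. Nine are changes in a Day 190 measurement, and eight of those name baseline as the reference. The tenth is "Percent change in number of falls during Weeks 13 to 24 from the number of falls during Weeks 1 to 12", met when the change is −20% or lower. It is the only one whose reference is an on-treatment window.

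The SAP gives no rule for a zero count in Weeks 1 to 12, for a partly observed Weeks 13 to 24, or for adjusting to time observed. The double-blind Falls text in SAP 4.7.2.2.1 states "No imputations will be performed for missing data". In SAP 4.2 the listed Per Protocol exclusion for early departure is "Patients who discontinue the study prior to the Dose 3 Day 43 visit; these patients may have been replaced per protocol", so later leavers are not removed on that ground.

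The principal falls analysis is separate: "The hazard ratio of recurring falls between ACE-083 and placebo between Weeks 1 and 24 will be estimated using the Andersen-Gill recurrent events model". Negative binomial regression is named there as a possible addition. Falls are an exploratory endpoint of Part 2. Before treatment, the only falls summary planned in SAP 4.4.2 is "Number and percent of patients who have fallen to the ground in the past 6 months", which is a yes/no history and not a count.

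**The concern.** A within-patient responder definition needs a reference that treatment has not touched. Here the reference begins at the first dose. If ACE-083 lowers the fall rate early and holds it down, both windows fall together and the ratio between them does not move. The criterion then measures timing of onset, not the amount of benefit.

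Two further problems come from using a ratio of raw counts. A patient with no falls in the first window has no percent change, and such patients become more common if the drug works. A patient who leaves partway through the second window has less time in which to fall.

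At stake is one exploratory p-value. A null result could be read as no effect on falls when the test had almost no chance of showing one, and it could sit beside a favourable Andersen-Gill estimate with no explanation.

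**Working it through.** **Inputs from the documents.** Dosing is every three weeks from Day 1. The arm size is taken as 18, the completers per arm in SAP 4.1.1. That figure reproduces (two-sided 0.10, difference 10, SD 10: power 90.2% by the noncentral t; 36/0.9 = 40 randomised), but it concerns muscle volume and is used here only as a sample size. The documents state no power, responder rate or fall rate for this criterion.

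**Assumptions.** Falls are gamma-Poisson with dispersion 1 and the same patient effect in both windows. The placebo mean μ is 1, 2 or 4 per 12 weeks, and the drug halves the rate. Some pure Poisson results, with means up to 6, are given for range.

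**Step 1, the reference window.** Weeks 1 to 12 are Days 1 to 84 (12 × 7). Planned doses on Days 1, 22, 43 and 64 fall inside; the Day 85 dose opens Week 13.

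**Step 2, the rule.** Let X be the count in Weeks 1–12 and Y the count in Weeks 13–24. Response is (Y − X)/X ≤ −0.20, that is Y ≤ 0.8X, defined only for X ≥ 1.

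**Step 3, what the ratio sees.** Let f1 and f2 be the drug's rate multipliers in the two windows. The ratio of expected counts is f2/f1:

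- placebo: 1/1 = 1
- halving from Week 1: 0.5/0.5 = 1
- halving from Week 7: f1 = (6 × 1 + 6 × 0.5)/12 = 0.75, so 0.5/0.75 = 0.67
- halving from Week 13: 0.5/1 = 0.5

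An early lasting benefit gives the same ratio as placebo. At μ = 4, with zero-fall patients counted as non-responders, responder rates are 34% on placebo and 32%, 48% and 61% on the drug for onset at Week 1, 7 and 13.

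**Step 4, unscorable patients.** With dispersion 1, P(X = 0) = 1/(1 + mean). For halving from Week 1:

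| μ | Placebo | Drug |
|---|---|---|
| 1 | 1/2 = 50% | 1/1.5 = 67% |
| 2 | 1/3 = 33% | 1/2 = 50% |
| 4 | 1/5 = 20% | 1/3 = 33% |

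**Step 5, the denominator.** Responder rates, placebo vs drug, halving from Week 1:

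| μ | Zero-fall patients as non-responders | Zero-fall patients excluded |
|---|---|---|
| 1 | 27.5% vs 21.1% | 55.0% vs 63.4% |
| 2 | 32.3% vs 27.5% | 48.4% vs 55.0% |
| 4 | 34% vs 32% | 43% vs 48% |

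The sign reverses with a choice the SAP leaves open. The assumed rate matters too: for pure Poisson falls with mean 6, counting zeros as non-responders gives 36.6% vs 41.0%.

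**Step 6, the test.** With 18 per arm, means 1 to 4, halving from Week 1 and zeros as non-responders, Fisher's test rejects in 5–8% of simulated trials and in the drug's favour in about 1–2%. With no effect it rejects in about 5–6%. With zeros excluded (20 per arm, means 1 to 6) it favours the drug in 5–8%. A rank test on the Weeks 13–24 counts, 18 per arm, rejects in 31–45%.

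**Step 7, leavers, if counts are taken as recorded.** With no drug effect and μ = 2, the chance that a scorable patient is called a responder is 48.4% with the second window fully observed, 60.7% with three quarters, 74.5% with half and 88.0% with a quarter. Leaving at Week 14 (2 of 12 weeks observed) gives 92–94% for means 1 to 4. Dropout of up to 10% of 20 is about 2 patients per arm.

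**The case against.** The strongest reply is that the falls question is answered elsewhere. The Andersen-Gill model compares the randomised arms directly over Weeks 1 to 24, and counts and numbers of fallers are also summarised by arm. This is one of ten secondary comparisons on an exploratory endpoint. That stands, and it limits the weight of the point. A reader might infer that the trial cannot tell whether ACE-083 reduces falls; the documents do not support that.

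Other limits also stand:

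- **Direction.** A reader might infer that the criterion scores an early-acting drug worse than placebo. That holds only under one handling of zero-fall patients, and not at every fall rate. With those patients excluded the drug arm scores higher, as a small-count artefact.
- **The rejection rate.** A figure below the nominal 10% might look perverse. Fisher's test is conservative at this size, and 5–8% is close to what it gives with no effect. The fault is lack of signal.
- **Early onset.** Protocol 7.2 reports a "mean increase from baseline in muscle volume of 14.5% and 8.9% for RF and TA, respectively" three weeks after the last of two doses. That is muscle volume in healthy post-menopausal women, and nothing links it to fewer falls by about Day 43. It makes an early effect plausible without showing one. If benefit on falls lags, the criterion can detect it.
- **Leavers.** That they score as responders is inferred. Doing no imputation is equally compatible with setting an incomplete window to missing.

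What the reply does not remove is that a planned significance test has a treated reference and an undefined value for an unknown share of patients.

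**Conclusion.** The point holds, at modest weight. Insensitivity to an early lasting reduction follows from the definition and needs no assumed fall rate, because the ratio of expected counts is 1 in both arms. The undefined value at zero and the missing rule are plain from the text. That an effective drug produces more zeros in Weeks 1 to 12 follows for any reduction acting in that window.

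The sizes are conditional. For a true halving from Week 1, under the stated model, the test rejects at about its null rate, while a direct comparison of the same second-window counts has roughly 31–45% power. The leaver effect is conditional on how incomplete windows are counted and involves about two patients per arm. The criterion can show a benefit that starts after Week 12, so it should not be called uninformative in all cases. It should be changed because its result cannot be interpreted without knowing when any benefit began.

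**What to change.** Delete the falls item from the Fisher list in SAP 4.7.2.3. Compare the randomised arms directly on falls in Weeks 13 to 24 per unit of observed time, by negative binomial regression with a log observed-time offset (SAP 4.7.2.2.1 already names the method), or by a rank test on the rate. Define observed time in the SAP and report how many patients have none in that window. Patients with no falls in Weeks 1 to 12 then need no special rule, and time after departure is not counted as fall-free.

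Do not substitute Fisher's test on any fall versus none in Weeks 13 to 24. Under the same assumptions it has only about 14–20% power, and it again favours early leavers.

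If the sponsor keeps the item as a description, it should carry no p-value, and the SAP should state the handling of zero counts and incomplete windows.

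The cost is SAP wording and one reprogrammed table; no new data are needed. The within-patient responder label for falls is lost. Little is lost for late onset: at μ = 4 and 18 per arm, with halving only from Week 13, the present criterion has about 40% power. The rank test on the Weeks 13–24 counts has about 43%, because those counts have the same distribution whether the halving began at Week 1 or Week 13.
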